5.4.3. Acid-reducing Agents

Avoid the concomitant use of proton pump inhibitors (PPIs) while taking pexidartinib. As an alternative to a PPI, administer pexidartinib 2 hours before or 2 hours after taking a locally-acting antacid, or if using a histamine 2 (H₂)-receptor antagonist, administer pexidartinib at least 2 hours before or 10 hours after taking an H₂-receptor antagonist.

5.5. Precautions and Restrictions

Because pexidartinib is a substrate for CYP3A4/5 and some fruits are CYP3A4/5 inhibitors, foods or beverages containing CYP3A4/5 inhibiting fruits (eg, grapefruit, pomelo, star fruit, and pomegranate) should be avoided throughout the study.

5.6. Blinding and Unblinding

Part 1 will be the placebo-controlled double-blind phase of the study where treatment assignment will remain unknown to the study subjects, Investigators, study site personnel, safety laboratory personnel, central imaging readers, and representatives of Daiichi Sankyo involved in the conduct and/or management of the trial. Pexidartinib and placebo capsules will be identical in appearance. All study treatment (pexidartinib or placebo) will be labeled with the study number, a unique number, and any additional information required in accordance with government regulations. Further details are contained in the separate Pharmacy Manual.

5.6.1. Unblinding

5.6.1.1. Emergency Unblinding

In the cases of emergency where, in the Investigator's opinion, immediate unblinding of the treatment is necessary in order to evaluate further course of action, the Investigator should access the interactive web/voice response system (IXRS) to initiate subject unblinding as follows:

IXRS Option 04: **Emergency Unblinding**

What to enter for each subject:

- Confirm to continue with unblinding
- Subject ID

What the IXRS will provide back to the site:

- Subject's randomized treatment arm
- IXRS transaction confirmation

The Investigator may also contact the Sponsor's Medical Monitor or designee for information related to pexidartinib adverse effects in making the decision to unblind. (Contact information – refer to Section 10.1.2.) It is important to note that, once unblinded, a subject cannot receive further study treatment and must discontinue from the study.

The Investigator should promptly document and report to the Sponsor any unblinding for emergency reasons (eg, accidental unblinding, unblinding due to an SAE) of the investigational product(s).

The "Emergency Unblinding" option should not be used for subjects who may need unblinding to move into Part 2 after the confirmed disease progression in Part 1. Please see the next section for more information.

5.6.1.2. Unblinding during Part 1 Week 13 to Week 25 for Disease Progression

In addition to the Emergency Unblinding option, if a central reading confirms RECIST 1.1-defined disease progression at or after Week 13 but before Week 25 visit, treatment assignment may be unblinded and potential continuation of a subject to Part 2 of the study will be assessed. If an investigator suspects disease progression during this period, an MRI should be submitted to the central reader with a request for an expedited read for potential disease progression. The investigator should alert the Sponsor and the Clinical Research Organization (Novella Clinical) Medical Monitors that the expedited read request has been made. Once the expedited read results are received, the investigator should discuss with the Sponsor and Novella Clinical Medical Monitors about the decision to unblind. If it is confirmed that the subject's study treatment should be unblinded, the Sponsor or designee will authorise the unblind in the IXRS system. Only once the Sponsor authorisation has been logged in IXRS can the site then unblind the subject, which will also be done through IXRS:

IXRS Option 04: **Part 1 Week 13 Unblind**

What to enter for each subject:

- Confirm to continue with unblinding
- Subject ID

What the IXRS will provide back to the site:

- Subject's randomized treatment arm
- IXRS transaction confirmation

DO NOT USE THE EMERGENCY UNBLIND FUNCTION FOR SUBJECTS WITH DISEASE PROGRESSION as they will not be able to receive further treatment and must discontinue from the study (as Emergency Unblinding cannot be undone).

Once in receipt of the unblind information, the site may then choose to continue the subject into Part 2 of the study or discontinue the subject from the study. Subjects receiving placebo will be eligible for early entry into Part 2 of the study. Effective 30 Sep 2016, subjects receiving placebo will be discontinued instead of being eligible to enter Part 2. Subjects receiving pexidartinib will be discontinued from the study unless the Investigator and the Sponsor's Medical Monitor judge that the subject would potentially benefit from continued treatment with pexidartinib.

For statistical analysis of endpoints at the end of Part 1, a clinical data cut-off date will be defined for the point when all randomized subjects complete or are discontinued from Part 1 with appropriate End of Part 1 follow-up. All data up to this date will be cleaned and locked. Afterwards, unblinding of database will be performed to facilitate the data analyses, including the data from the double-blind Part 1 and available data from Part 2. Such unblinding is only intended for the sponsor and the Contract Research Organization. Subjects who entered Part 2 may continue to receive open-label pexidartinib treatment. Updated analysis of Part 2 data only, in the form of summary and descriptive statistics, will be performed at the end of the trial. Additional updates between the above-mentioned cut-off and end of the trial may also be performed.

5.6.1.3. Unblinding at the End of Part 1

As of 30 Sep 2016, subjects on placebo in Part 1 are no longer allowed to enter Part 2 to receive open-label pexidartinib. After completion of the end of Part 1 assessments (Part 1 Completion visit/Early Termination visit), subjects who wish to continue onto the open label part of this study (Part 2) will be unblinded and those on placebo will be discontinued; subjects on pexidartinib in Part 1 may continue into Part 2 to continue to receive pexidartinib. (Detailed instructions will be provided separately.)

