MRIs will be performed at Week 13 (Cycle 4, Day 1 visit of Part 1 [P1-C4D1]) and Week 25. If disease progression is indicated clinically or by local radiologic assessment according to RECIST 1.1 at or after Week 13 but before Week 25, the Investigator may request a central review for evaluation of disease progression. Any disease progression before Week 25 must be verified by a central MRI reading. If a central reading confirms RECIST 1.1-defined disease progression, treatment assignment will be unblinded, and subjects receiving placebo will be eligible for early entry into Part 2 of the study. Effective 30 Sep 2016, subjects receiving placebo will be discontinued instead of being eligible to enter Part 2. Subjects receiving pexidartinib will be discontinued from the study unless the Investigator and the Sponsor's Medical Monitor judge that the subject would potentially benefit from continued treatment with pexidartinib. For those subjects who undergo surgical resection after Week 25, an MRI will be performed 4 months after surgery.

Part 2 will continue until all subjects have either reached at least the Week 49 visit, ie, an additional 24 weeks of study treatment beyond the placebo-controlled phase, or withdrawn from the trial (Figure 3.1). As in Part 1, dose reductions, interruptions, and re-escalations after previous reductions for toxicity are permitted according to pre-specified guidelines. Subjects who complete Part 2 will be eligible to continue pexidartinib treatment for study of longer efficacy and safety follow-up assessed per the schedule in Part 2 or to enter a separate protocol to continue receiving pexidartinib.

Figure 3.1: Study Schematic*

* Effective 30 Sep 2016, subjects on placebo are no longer allowed into Part 2 to receive open-label pexidartinib.

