4.2.2. Withdrawal Procedures

When a subject discontinues or is permanently withdrawn from the study, the Investigator will notify the Sponsor and ensure that the procedures listed in the 28 Day "Post-treatment Visit" column in the Schedule of Events ([Table 15.2](#) and [Table 15.3](#)) are performed 28 ± 7 days after the

subject's last dose of study treatment and prior to initiating any new PVNS/GCT-TS therapy, including surgery.

The consequence of a subject's withdrawal of all consent will be that no new information will be collected from that subject and added to the existing data or any database. However, every effort will be made to follow all subjects for safety.

The reason for study withdrawal will be recorded. If a subject discontinues study treatment to undergo surgery, information about the type of surgery and its outcome will be collected.

If a subject discontinues study treatment before the end of Part 1, the end of Part 1 assessments (Part 1 Completion visit/Early Termination visit) should be performed at the time of early discontinuation (Table 15.2). These subjects will not be unblinded.

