15.3.1. Part 2–Cycle 1, Day 1 (P2-C1D1; Week 25)

For subjects continuing to Part 2, the P2-C1D1 visit will serve as both the Part 1 Completion visit and the first visit of Part 2. Some procedures for both visits can occur on the same day.

The following procedures are performed as part of the P1-Completion visit.

To be performed within the 7-day period *before* the P2-C1D1 visit:

- ECHO or MUGA scanning;
- MRI of the affected joint (with local assessment of progression status). The Investigator may request a centrally read MRI to confirm progression, eg, if a subject's mid-study clinical profile or local radiological assessment indicates progression.
- Third-party blinded range-of-motion assessment of the affected joint.

To be performed *before* any invasive procedures:

- Vital signs, including blood pressure, pulse rate, and oral temperature;
- PRO instruments, in the following order:
 - BPI Worst Pain NRS item;
 - Worst Stiffness NRS item;
 - PROMIS Physical Function Scale;
 - EQ-5D-5L.

To be performed *before* dosing at the P2-C1D1 visit:

- Review outpatient PRO instruments;

- AE assessment;
- Concomitant medications, including analgesics;
- Treatment compliance assessment;
- Analgesic use assessment.
- Weight;
- Physical examination;
- Clinical laboratory tests - serum chemistry, hematology, coagulation, liver function, hormone levels, serum pregnancy testing (as applicable), urinalysis.

Note: Women who are not using hormonal contraception will be tested for levels of FSH, LH, progesterone, and estradiol. Hormone testing will not be required for women who have either had an oophorectomy or are post-menopausal. Men will be tested for levels of LH, FSH, and testosterone. Men whose testosterone level is below baseline at the last study visit should be followed until their level has stabilized or returned to baseline.

- Surgical Assessment Questionnaire.

The following procedures will be performed as part of the P2-C1D1 visit.

To be performed *before* dosing:

- Blood sampling for PK and PDy analysis

Subject is dosed in clinic.

To be performed *after* dosing:

- Record the dose (subject diary, source records, eCRF);
- Dispense study treatment bottles.

To be performed 2 hours \pm 10 minutes *after* dosing:

- 12-lead ECG.

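### Section 5.6.1.2 does not require the end-of-Part-1 patient-reported and range-of-motion assessments before progression unblinding, and no rule covers scores recorded after it

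*Combined protocol and SAP*

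**What the plan says.** **Progression path.** Section 5.6.1.2 provides that "if a central reading confirms RECIST 1.1-defined disease progression at or after Week 13 but before Week 25 visit, treatment assignment may be unblinded". The sponsor authorises, the site unblinds in IXRS, and then: "Once in receipt of the unblind information, the site may then choose to continue the subject into Part 2 of the study". The alternative at that step is discontinuation. For placebo, "Effective 30 Sep 2016, subjects receiving placebo will be discontinued instead of being eligible to enter Part 2". A pexidartinib subject leaves unless the investigator and the medical monitor see potential benefit in continuing. Sections 3.1 and 6.4.9 word the trigger more firmly; Section 3.1 has "treatment assignment will be unblinded, and subjects receiving placebo will be eligible for early entry into Part 2".

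**Early discontinuation.** Section 4.2.2 calls for the end-of-Part-1 assessments when treatment stops early, and adds "These subjects will not be unblinded". Section 15.2.16 and Table 15.2 footnote c ask for them no later than the last treatment. They waive a repeat MRI or range-of-motion assessment if one was done in the preceding 28 days.

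**Entry to Part 2.** Section 5.6.1.3 sets the order: "After completion of the end of Part 1 assessments (Part 1 Completion visit/Early Termination visit), subjects who wish to continue onto the open label part" are unblinded. Section 15.2.16 and Table 15.2 footnote c say the same. Under Section 15.3.1, "the P2-C1D1 visit will serve as both the Part 1 Completion visit and the first visit of Part 2".

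**Analysis.** Section 7.3 gives the MMRM every measurement available from each subject. Section 7.4 limits the Week 25 comparison to visits between baseline and Week 25. In the fixed sequence of Section 7.6.2, range of motion is secondary endpoint 1, Tumor Volume Score response 2, PROMIS 3, Worst Stiffness 4 and BPI-30 response 5.

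**The concern.** Three of the five gated secondary endpoints (PROMIS, Worst Stiffness, BPI-30) are the subject's own report. Their value as blinded evidence depends on the subject not knowing the assignment when answering. On the progression path the protocol leaves that to site timing. A site can follow Sections 5.6.1.2 and 4.2.2 as written and collect the last Part 1 scores from someone who has just been told the assignment and whether they will stay in the study.

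The analysis sections do not identify such scores, so they would be treated like any blinded score. Because testing is sequential, a distorted result on endpoint 3 or 4 also decides whether later endpoints are tested at all.

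**Working it through.** **1. Order of events.** Section 5.6.1.2 runs: central read, sponsor authorisation, IXRS unblind, decision to continue or discontinue. Section 4.2.2 ties the early-termination assessments to discontinuation. If discontinuation is decided after the unblind, assessments made at that point are unblinded. The outer limit in Section 15.2.16 (no later than the last treatment) permits earlier assessment but does not require it before the unblind.

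**2. Conflicts between sections.**
- Section 5.6.1.3, Section 15.2.16 and Table 15.2 footnote c put the assessments first and name the Early Termination visit, but for subjects who wish to enter Part 2. On the progression path that choice follows the unblind.
- Section 4.2.2 excludes unblinding of early discontinuers, with no exception. A placebo subject with confirmed progression is unblinded and then discontinued.
- Emergency unblinding (Section 5.6.1.1) also forces discontinuation, so it meets the same conflict.
- Section 5.6.1.2 says assignment *may* be unblinded; Sections 3.1 and 6.4.9 say it *will* be.

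**3. Which data are exposed.**
- PROMIS, Worst Stiffness and BPI are scheduled on treatment at Weeks 9, 17 and 25 (Table 15.2). A subject unblinded after the Week 13 scan and before Week 17 has Week 9 and then only the termination visit. The 28-day waiver does not cover these instruments.
- Pain and stiffness also use diary days before the visit, some of which may predate the unblind.
- Range of motion is measured by a blinded third party (Section 6.4.4), and a Week 13 measurement may stand under the 28-day waiver. Only the subject's own knowledge could affect a new one.
- The primary and Tumor Volume Score endpoints rest on central reads blinded to assignment.

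**4. Entry into the comparison.** Completion and early termination share one Table 15.2 column headed Week 25. The document does not say which time point an early-termination score is assigned to, or how a score dated after unblinding is handled. Sections 7.4 and 7.6.2 refer to a SAP for details; no such rule appears in the document.

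**5. Size.** The plan's own figure is 90% power for the primary endpoint (63 per arm, 10% versus 35%, two-sided Fisher's exact test at 0.05; Section 7.12). Exact enumeration gives 90.6%, so it reproduces, and this point does not change it.

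For a mean score on the 0 to 10 scale, if k of the 63 subjects in an arm each give a value shifted by d points, the simple arm mean moves by k × d / 63. The documents give neither k nor d. Assumed ranges are k = 1 to 6 and d = 0.5 to 2:

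| k | Share of arm | d = 0.5 | d = 2 |
|---|---|---|---|
| 1 | 1.6% | 0.008 | 0.032 |
| 3 | 4.8% | 0.024 | 0.095 |
| 6 | 9.5% | 0.048 | 0.190 |

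This treats every shifted score as a Week 25 value and ignores the MMRM weighting. The standard deviations needed to turn the shift into a test statistic are not given.

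**The case against.** The strongest reply is that Section 5.6.1.2 is silent on order, and that three other places state assessments first and name the Early Termination visit. A careful site could apply that order throughout. This stands against a reader who infers that the protocol orders unblinding before assessment: it does not. It does not close the gap, because those statements address subjects wishing to enter Part 2, and on this path that is settled after the unblind.

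Other stronger readings also fail:
- *Open-label results enter the comparison.* Section 6.4.8 places the instruments before the morning dose on visit days, and placebo subjects with progression have been discontinued since 30 Sep 2016. Their scores could be unblinded, but would not be open-label.
- *The scores certainly count as Week 25.* A shared schedule column is not an analysis window. Their entry is inferred from the absence of a rule.
- *The bias always favours pexidartinib.* A placebo subject may report worse on learning the assignment. But the default for a progressing pexidartinib subject is also discontinuation, and that subject may report worse too.

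The path is probably narrow. Section 1.1.1 describes slow progression, and unblinding needs an investigator's request, central confirmation and sponsor authorisation. That supports a small effect. It does not remove the contradiction with Section 4.2.2.

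**Conclusion.** The concern holds as a gap and a set of conflicts. Section 5.6.1.2 does not require the end-of-Part-1 assessments before progression unblinding. Read with Section 4.2.2, it allows self-reported stiffness, function and pain to be recorded with knowledge of assignment, and nothing in the document keeps those scores out of the Part 1 comparisons. Section 4.2.2 contradicts Section 5.6.1.2, and the *may* and *will* wordings disagree.

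Exposure is mainly in PROMIS, Worst Stiffness and BPI, and weaker for range of motion. The primary and Tumor Volume Score endpoints are unaffected. The direction of any bias is not determined. The 0.01 to 0.19 point range is an illustration resting wholly on the assumed number of subjects and the assumed shift. The case for acting is that the gap is avoidable and concerns gated endpoints, not that the effect has been shown to be large.

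**What to change.** 1. In Section 5.6.1.2, make completion of the end-of-Part-1 visit instruments, and of range of motion if due under the 28-day rule, a condition of the sponsor's IXRS authorisation for non-emergency progression unblinding. Use the diary days already available, so that unblinding is not held for a full 7-day diary.
2. Reconcile Sections 3.1, 4.2.2, 5.6.1.2, 5.6.1.3 and 6.4.9 and Table 15.2 footnote c. Give Section 4.2.2 an exception for progression and emergency unblinding, and use one wording for whether progression leads to unblinding.
3. State the time point to which an early-termination visit, or an early P2-C1D1 visit, is assigned.
4. Flag patient-reported and range-of-motion values dated after any unblinding, emergency unblinding included. Keep the planned primary handling and add a sensitivity analysis without those values. For emergency unblinding this flag is the only remedy, since reordering cannot apply.

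Exclusion should not be the main analysis. Removed BPI data would count as non-response under Sections 7.3 and 7.6.2; if progression is commoner on placebo, that would itself favour pexidartinib.

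The cost is a short delay before non-emergency unblinding, one authorisation check, text corrections and one sensitivity analysis.

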5.7. Description of Investigational Agents

Pexidartinib (PLX3397)

Pexidartinib is an HCl salt with a white to off-white crystalline solid appearance. PLX3397 HCl capsules are provided as 200 mg (200 mg free base equivalent) hypromellose capsules for oral administration containing the following excipients: Poloxamer 407, mannitol, crospovidone and magnesium stearate. Formulation of pexidartinib is J-3397-AF in hydroxypropyl methylcellulose capsules.

Placebo

The matching placebo capsules for oral administration contain Poloxamer 407, mannitol, crospovidone and magnesium stearate only, with an increased amount of mannitol to adjust for the absence of the active pharmaceutical ingredient.

5.8. Packaging and Labeling

PLX3397-HCl 200 mg capsules and placebo capsules are manufactured, packaged, and labeled according to Good Manufacturing Practices and Good Clinical Practices (GCP) at the following address:

Catalent Pharma Solutions, Inc.
[name]
[name]
USA

5.9. Storage, Handling, and Accountability

Study treatment (pexidartinib and placebo) in accordance with this protocol should be stored at the sites in a secure controlled facility and only provided to subjects who signed a consent form and are participating in the study. The study treatment must be stored at room temperature (do not store above 25°C/77°F). Excursions are permitted from 15°C to 30°C (59°F to 86°F), however approval for continued use must be obtained from Daiichi Sankyo for excursions <15 °C or ≥25°C (77°F). Subjects will be instructed to store the study treatment at room temperature out of the reach of children or other cohabitants.

The Food and Drug Administration and other health authorities require accurate and up-to-date accounting of the disposition of all study treatment received by the site. Records of study treatment disposition required by federal law include the dates and quantities received from the Sponsor, the dates and quantities administered to a subject, including the identity of the subject, the dates and quantities returned by a subject (if applicable), and the dates and quantities of final disposition (ie, dates/quantities that unused study treatment is returned to the Sponsor/designee or dates/quantities that unused study treatment is destroyed on-site/off-site as applicable in accordance with GCP and site standard operating procedures). For any study treatment that is destroyed, destruction details must be documented on accountability and destruction logs and include at a minimum the number of bottles and capsules destroyed, batch number (if applicable), and the date and method of destruction. Any study treatment accidentally or deliberately destroyed must be recorded in a timely fashion, including an explanation for the destruction in writing. Any discrepancies between the amounts of study treatment dispensed and returned must also be explained in writing.

The Investigator is responsible for the overall accountability and accurate and up-to-date documentation/disposition of all unused and used study treatment supplied by the Sponsor.

Dosage form (ie, capsules) site level accountability documentation is to be included with each drug supply return shipment (or other returning facility, such as another depot). This is required as part of the receiving records for return shipments.

Dosage form (ie, capsules) site level accountability documentation is required as part of the disposition records of IP. The dosage form site level accountability documentation should be appended to the Certificate of Destruction.

